9.8.3. Deaths

9.8.4. Clinical Laboratory Evaluations

For laboratory tests although reported in the NCI CTCAE scale such as eosinophils, glucose (hyperglycemia), sodium (hyponatremia), potassium (hypokalemia) and amylase (increased), for which the grading system is based mainly on clinical assessments, the grade will not be calculated.

Statistical Analysis Plan

Summary tables of NCI-CTCAE grade from baseline to worst post baseline grade (cycle 1, cycle>1, any cycle) will be provided. Selected laboratory parameters will be further explored by analyzing the nadir/zenith values, the time to nadir/zenith, and the time to recovery after nadir/zenith, as clinically indicated.

For the other abnormal laboratory parameters not graded by NCI CTCAE scale, results will be classified as low (L) or high (H), according to the laboratory reference ranges. In case both type of abnormal measures will be observed during study for the same subject, the occurrence will be counted for each abnormality. The number and percentage of patients who show measurements below and/or above reference range will be summarized for the following laboratory parameters:

- Hematology: monocytes, eosinophils, basophils, blast cells,
- Blood chemistry: glucose (only for hyperglycemia), sodium (only for hyponatremia), potassium (only for hypokalemia), uric acid, total protein, blood urea nitrogen, urea, total protein, direct bilirubin, lipase and amylase

Coagulation: Prothrombin Time (PT) and Partial Thromboplastin Time (PTT), International Normalized Ratio (INR) and Partial Thromboplastin Time/Ratio (aPTT).

Laboratory results (hematology, blood chemistry, coagulation) will be listed for all treated patients by study phase, assigned schedule and dose level at each visit. All other parameters collected on the eCRF, i.e., urinalysis and pregnancy tests, will be listed in dedicated listings presenting all corresponding collected information on the eCRF.

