## 11.5. Safety Assessments

Safety assessments include collection of AEs, SAEs, triplicate 12-lead ECGs, vital sign measurements, physical examinations and safety laboratory tests. These will be performed periodically at baseline, during treatment and at End of Treatment (and/or at Investigators' discretion).

Assessment of adverse events will include type, incidence, severity (graded by the National Cancer Institute [NCI] Common Terminology Criteria for Adverse Events [CTCAE], Version 5.0), timing, seriousness, and relatedness.

Baseline signs and symptoms will be recorded at baseline and then reported as adverse events during the trial if they worsen in severity or increase in frequency.

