8.2. Analysis Conventions

All collected data will be presented in listings. Data not subject to analyses according to this plan will not appear in any tables or graphics but will be included only in the data listings. Partial dates in principle will not be imputed except for date of birth. Only year of birth will be collected in the database and to estimate patient's age, December 31st will be used to replace the missing month and day, respectively.

Study day will be calculated in reference to the date of first study treatment. The study day will be displayed in all relevant data listings.

The baseline visit will correspond to the last assessment with non-missing result performed before initial study drug administration, unless otherwise indicated in the appendix TLGs Mock-ups and Algorithms.

All analysis conventions are detailed in the separate appendix TLGs Mock-ups and Algorithms.

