9.8.5. Other Safety Evaluations (e.g., Vital signs, ECG, ECOG PS, etc.)

Descriptive summaries of actual values and changes from baseline will be presented for all vital signs (systolic blood pressure, diastolic blood pressure and pulse), and weight.

Descriptive summaries of actual values and changes from baseline will be presented for the following ECG parameters: sinus rhythm, heart rate (HR), RR interval, PR interval (PR), QRS interval, QT interval and corrected Fridericia QT interval (QTcF). Additionally, for these ECG parameters, the worst assessment on treatment versus baseline, defined in terms of classes, will be summarized by shift table. Frequency and percentage of treated patients with at least one clinically significant ECG abnormality during the treatment period will be summarized by category of ECG abnormalities. Such analyses will be performed also for Physical Examinations and ECOG Performance Status.

[REDACTED]

[REDACTED]

Statistical Analysis Plan

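### The summary of ungraded laboratory tests in SAP 9.8.4 takes no account of baseline, so it mixes abnormalities present at entry with new ones

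*SAP*

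**What the plan says.** SAP 9.8.4 handles laboratory tests in two ways.

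- **Graded tests.** "Summary tables of NCI-CTCAE grade from baseline to worst post baseline grade (cycle 1, cycle>1, any cycle) will be provided". This is a comparison with baseline.
- **Ungraded tests.** For these, "results will be classified as low (L) or high (H), according to the laboratory reference ranges". The summary is then a count of patients: "The number and percentage of patients who show measurements below and/or above reference range will be summarized for the following laboratory parameters". The list opens with "Hematology: monocytes, eosinophils, basophils, blast cells" and goes on to chemistry and coagulation tests. Glucose, sodium and potassium are counted in one direction only.

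The only time reference for the ungraded tests is in the rule for patients with both kinds of abnormality: "In case both type of abnormal measures will be observed during study for the same subject, the occurrence will be counted for each abnormality".

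The SAP already has what a baseline comparison needs. Section 8.2 defines baseline: "The baseline visit will correspond to the last assessment with non-missing result performed before initial study drug administration". For ECG parameters, section 9.8.5 states that "the worst assessment on treatment versus baseline, defined in terms of classes, will be summarized by shift table", and it summarizes vital signs as changes from baseline.

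**The concern.** Laboratory abnormalities are part of the secondary safety endpoint (SAP 3.2.2). The study is non-randomised and has no control group, so a patient's own baseline is the only internal reference that separates disease at entry from change on treatment.

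Some of the listed tests measure the disease itself. The protocol's response criteria use them that way: AML complete remission requires absence of circulating blasts (Appendix 2.1), and CMML complete response sets limits on blood blasts and monocytes (Appendix 3). A count that ignores baseline gives the same result for a patient who arrives with circulating blasts as for one in whom they newly appear. A reader of the safety table could take the first for an on-treatment finding, and a real change could be harder to see.

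**Working it through.** The plan states no figure on this point, so there is nothing to reproduce. The check is a comparison of the rules, then an illustration.

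**1. Baseline reference in the safety summaries**

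| Data | Section | Reference to baseline |
|---|---|---|
| Graded laboratory tests | SAP 9.8.4 | Baseline grade to worst post-baseline grade |
| Ungraded laboratory tests | SAP 9.8.4 | None stated |
| ECG parameters | SAP 9.8.5 | Shift table against baseline |
| Vital signs | SAP 9.8.5 | Change from baseline |
| Events present before treatment | SAP 9.8.1 | Treatment-emergent only if they worsen |

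The ungraded laboratory tests are the exception.

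**2. Three patient records under the written rule**

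| Record | As written | With a baseline shift |
|---|---|---|
| Blasts high at screening, then falling on drug but still high at one post-baseline test | High | High to high |
| Monocytes high at baseline and unchanged | High | High to high |
| Uric acid normal at baseline, then high | High | Normal to high: newly high |

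All three receive the same entry, and only the third is new. Limiting the count to post-baseline values would not be enough, because the first two patients still have a high value after baseline.

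**3. Illustration of the mixing**

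For one test and one direction, let

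- q = share of patients out of range at baseline who are counted in the table;
- r = share of the remaining patients who become out of range.

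Crude share = q + (1 − q) × r. Share of the count that was pre-existing = q / crude share.

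Both q and r are assumptions; the documents give neither. The only document figure is n = 40, the planned size of a Phase II cohort (SAP 4.1). With r = 10%:

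| q | Crude share | Patients of 40 | New cases / patients at risk | Pre-existing share of count |
|---|---|---|---|---|
| 0% | 0 + 1.0 × 0.10 = 10% | 4.0 | 4.0 / 40 | 0% |
| 30% | 0.30 + 0.70 × 0.10 = 37% | 14.8 | 2.8 / 28 | 81% |
| 50% | 0.50 + 0.50 × 0.10 = 55% | 22.0 | 2.0 / 20 | 91% |
| 70% | 0.70 + 0.30 × 0.10 = 73% | 29.2 | 1.2 / 12 | 96% |
| 90% | 0.90 + 0.10 × 0.10 = 91% | 36.4 | 0.4 / 4 | 99% |

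Across q = 30% to 90% and r = 0% to 20%, the crude share runs from 30% (0.30 + 0.70 × 0) to 92% (0.90 + 0.10 × 0.20). The pre-existing part of the count runs from 68% (0.30 / 0.44) to 100%. The new-onset rate among patients at risk is r throughout, and the crude table does not show it.

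The first row matters as much as the others. For a test that is rarely abnormal at entry, the crude count is close to the new-onset count and little is lost.

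**The case against.** **The missing text could settle it.** SAP 8.2 refers analysis conventions to a separate appendix of mock-ups and algorithms, which is not among the documents. Protocol 12.3.6 is redacted, and the visible text of SAP 9.8.4 opens on an exception, so introductory wording may be absent. The time reference quoted above does not expressly bring in screening values. This stands as a caution: a baseline split may exist elsewhere. Even so, the paragraph on ungraded tests reads as complete, and the SAP puts the baseline comparison in its main text for graded tests and ECG but not here.

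**Other outputs cover part of the need.** Results are listed by visit for all treated patients, selected parameters may have nadir or zenith analyses, and blast clearance is judged by the response criteria. This also stands in part. Listings are not summaries, however, and the nadir or zenith analyses are optional.

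**Stronger readings that the documents do not support**

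- A reader might infer a contradiction with Protocol 11.5, which says "Baseline signs and symptoms will be recorded at baseline and then reported as adverse events during the trial if they worsen in severity or increase" (that is, become more frequent). That sentence governs when signs and symptoms are reported as adverse events. It does not govern a descriptive laboratory table.
- A reader might infer that adverse-event counts are inflated. They are not. Protocol 11.5.1.8 sets separate conditions for reporting laboratory findings as events, and SAP 9.8.1 requires worsening of events already present.
- A reader might infer that the table cannot show a signal for lipase, direct bilirubin or coagulation. The documents give no entry abnormality rates for these tests. For liver function, eligibility limits transaminases, alkaline phosphatase and total bilirubin at entry (Protocol 6.1).

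**Conclusion.** The point holds within narrow limits. As written, SAP 9.8.4 counts out-of-range values of ungraded tests without baseline class and without an explicit post-baseline limit, unlike the graded tests beside it and the ECG analysis that follows. In this single-arm trial the resulting table mixes disease at entry with change on treatment. The case is strongest for blast cells and monocytes and weaker for chemistry and coagulation.

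Its size cannot be stated from the documents. The percentages in the illustration depend wholly on the assumed q and r and are not estimates for this trial. The effect is confined to one descriptive safety table; error rates, sample size, the primary endpoint and the safety stopping rules are untouched. The conclusion also assumes that the separate mock-up appendix does not already add a baseline split. The change is worth making because it is nearly free and brings this table into line with the rest of the safety analysis.

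**What to change.** In SAP 9.8.4, replace the crude count for ungraded tests as follows:

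1. State that only post-baseline values count, with baseline as defined in SAP 8.2.
2. Tabulate baseline class (low, normal, high) against any post-baseline low and, in a separate panel, any post-baseline high, for cycle 1, cycles after 1 and any cycle. Two panels keep the existing rule that a patient with both abnormalities is counted for each.
3. Add the percentage newly low or newly high, with patients not in that class at baseline as the denominator.
4. Keep the one-direction rule for glucose, sodium and potassium.

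The newly abnormal percentage will still include chance crossings of the reference limits over repeated tests, so it should be read descriptively.

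The cost is one SAP sentence and one table shell, with no new data. If the mock-up appendix already has this layout, only the SAP sentence is needed.

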9.8.5. Other Safety Evaluations (e.g., Vital signs, ECG, ECOG PS, etc.)

Descriptive summaries of actual values and changes from baseline will be presented for all vital signs (systolic blood pressure, diastolic blood pressure and pulse), and weight.

Descriptive summaries of actual values and changes from baseline will be presented for the following ECG parameters: sinus rhythm, heart rate (HR), RR interval, PR interval (PR), QRS interval, QT interval and corrected Fridericia QT interval (QTcF). Additionally, for these ECG parameters, the worst assessment on treatment versus baseline, defined in terms of classes, will be summarized by shift table. Frequency and percentage of treated patients with at least one clinically significant ECG abnormality during the treatment period will be summarized by category of ECG abnormalities. Such analyses will be performed also for Physical Examinations and ECOG Performance Status.

[REDACTED]

[REDACTED]

Statistical Analysis Plan

11. APPENDICES

The appendix “TLGs Mock-ups and Algorithms” is provided as a separate document.

Statistical Analysis Plan

13. VERSION HISTORY

Version N°	Effective Date	Changes from the Previous Version
1.0	18-Dec-2020	Initial Version.
2.0	17-Nov-2021	Version related to Protocol version 5.0 and eCRF version 3.0
3.0	28-Mar-2024	Details of changes are specified in Section 2.1
